3.0 Background and Significance

Outpatient knee arthroscopy is considered a common procedure in the United States with more than 500,000 surgeries performed on an outpatient basis yearly.[29] Immediate post-operative pain has multiple etiologic factors including the type of surgery performed, operative time, and time from surgery among others.[30] Unfortunately, these factors are non-modifiable. Therefore, post-operative pain in the ambulatory setting is inevitable.[31-33] Limiting narcotic analgesic

usage has several advantages and thus strategies to accomplish this goal have been proposed for major orthopaedic surgery.[31]

TENS has been offered as an adjunct to analgesic use in the early post-operative period in a variety of settings. In a prospective, randomized study, Briet and Van der Wall compared narcotic analgesic usage following total knee arthroplasty with and without the use of TENS therapy. The authors were unable to demonstrate significant reductions in post-operative analgesic requirements with the use of TENS therapy following total knee arthroplasty.[1] In a prospective randomized clinical trial following abdominal surgery however, Cooperman and colleagues found that 77% of patients receiving TENS therapy in the immediate post-operative period reported good or excellent results, while 33% of patients reported good to excellent pain control without TENS.[9]

For the non-operative treatment of knee osteoarthritis, TENS therapy has seen mixed results. When compared to intraarticular hyaluronic acid, TENS therapy has shown no statistically significant difference in pain and functional outcome at 6 months following treatment.[15] Law et al. demonstrated significant improvements in self-reported pain and ROM in first two weeks following initiation of a TENS therapy program for patients with osteoarthritis. They were unable to detect differences in patient-oriented outcomes.[18] Cheing et al. found that four weeks of TENS therapy for knee osteoarthritis resulted in improved pain measures, but the treatment was not statistically different than placebo or exercise alone.[24] In a Cochrane Review of 6 trials, Osiri et al concluded that TENS is more effective than placebo for the treatment of knee osteoarthritis.[25] In the setting of rheumatoid arthritis, Casamiro and colleagues in a Cochrane Review found that TENS was effective for pain control, but a formal recommendation for its use was precluded by the poor design of the studies included.[17]

4.0 Preliminary Studies

Preliminary data is pending.

5.0 Research Design and Methods

5.1 Rationale for use of hand-held dynamometer

The reliability and validity of hand-held dynamometry has been extensively studied and adopted as a means of efficiently determining quadriceps strength in the outpatient setting.[34-45]

5.2 Rationale for use of outcomes instruments

Outcomes measures have been extensively used in orthopaedic research.[46] The KOOS (Knee Injury and Osteoarthritis Outcomes Score) evaluates five dimensions and is specific to knee-related pathology: pain, symptoms, ADLs, sports and recreation function, and knee-related quality of life. The Marx Activity Level Scale consists of four questions and was designed to be a short, patient-reported activity assessment that can be used in addition to knee rating scales and general health outcomes measures. The Lysholm knee scale was developed for the followup evaluation of knee ligament surgery, with an emphasis on symptoms of instability. It consists of eight items (limp, support, stair climbing, squatting, instability, locking and catching, pain, [name] 4.2011

swelling). It is included for historical comparison and perspective. The IKDC (International Knee Documentation Committee) scale is a subjective form consisting of 18 questions. This form is considered to be specific to the knee and widely used in outcomes research. The SF-12 is a shortened version of the SF-36 and is a general health quality of life instrument.

6.0 Inclusion/Exclusion Criteria

- Age 18-60
- BMI ≤ 50
- No significant joint malalignment
 - Neutral to 5° valgus alignment as measured on standing weight-bearing PA radiographs of the knee or standing extremity alignment radiographs.
- No significant ligamentous instability.
 - Normal Lachman, pivot shift, varus and valgus stress tests.
- No significant radiographic joint space narrowing
 - Joint space measurement within 10% in each compartment as measured by digital radiography in standing weight-bearing view.
- No prior significant knee surgery
 - No prior ligamentous or osteotomy surgery
 - Prior partial meniscectomy is acceptable
- Unilateral knee surgery
- Not Worker's Compensation
- Planned knee arthroscopy for meniscectomy, chondroplasty, or synovectomy

7.0 Randomization Procedure

Patients will be randomized using a block randomization scheme generated by the statistician. Sealed envelopes will be used to conceal the random assignments of patients to one of two treatment groups in the immediate post-operative period.

- Group 1: structured TENS therapy (n=10)
- Group 2: sham TENS therapy (n=10)

8.0 Patient Form (Week 1 and 2 post-operative)

Patients will complete a pain and analgesic usage diary. Additionally, patients will complete VAS pain questions daily and pre- and post-TENS treatment. See Appendix D. TENS treatment will be standardized and will consist of 20 minute sessions three times per day at the manufacturer's recommended settings.

9.0 Proposed Timeline

- Pre-study: Patient questionnaire and database constructed.
- 0-3 months: Patient enrollment begins.
- 3-9 months: Data collection. Initial data analysis of immediate post-operative pain logs.
- 9-12 months: Data analysis.
- 12-14 months: Pilot study completion and preparation for multi-center study. Power analysis will be performed to determine the number of patients needed to enroll.

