1.0 Abstract

Introduction

Transcutaneous Electrical Nerve Stimulation (TENS) therapy has been used for the control of postoperative pain with variable results.[1-9] TENS therapy is also considered an appropriate non-pharmacologic adjunct to patient care in the setting of symptomatic knee arthritis.[10-28] Recently, orthopaedic surgeons have begun to utilize TENS therapy about the operative site in the early post-operative period because of several proposed benefits including pain relief with decreased analgesic requirements, increased quadriceps strength with decreased postoperative muscle atrophy. To our knowledge, the use of TENS as an adjunct to post-operative analgesia in the setting of outpatient knee arthroscopy has not been extensively studied. We propose a pilot study to determine the effectiveness of TENS therapy in the early post-operative period following knee arthroscopy for meniscectomy, synovectomy, or chondroplasty.

Methods

Consecutive patients meeting inclusion criteria will be randomized to one of two treatment groups: 1) structured TENS therapy (n=10) or 2) sham TENS therapy (n=10). Patients and the surgeon will be blinded to the TENS treatment group. Patients will complete preoperative assessments of pain and function using standardized outcomes instruments, then complete daily pain assessments and reports of analgesic consumption in the early post-operative period (two weeks). TENS will be discontinued at two weeks post-operatively. The surgeon will complete the IKDC Surgical Document Form with information from the surgical procedure. Patients will be followed for a total of six months post-operatively with clinical measurements of quadriceps strength, knee range of motion, presence of effusion, and quadriceps circumference (measure of atrophy). Functional outcomes will be measured with KOOS, Marx, Lysholm, IKDC, and SF-12 for up to six

months post-operatively. Statistical analysis will be performed using computer software and significance defined as $p < 0.05$.

The results of the pilot study will be used to design a multi-center prospective randomized clinical trial.

Conclusion

TENS therapy in the early post-operative period following outpatient knee arthroscopy has not been extensively studied. This pilot study will provide initial information for the effectiveness of this widely-used clinical device.

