2.0 Specific Aims

Transcutaneous Electrical Nerve Stimulation (TENS) therapy has been used for control of knee pain with good results. Documented benefits of non-pharmacologic post-surgical pain control using TENS include decreased opioid analgesic usage, increased muscle strength, with a relative lack of side-effects.[1-9] Additionally, TENS therapy has been studied extensively for the nonoperative treatment of knee arthritic conditions with somewhat mixed results.

Knee arthroscopy in the outpatient setting often requires a patient's pain to be well controlled in order to ensure day of surgery discharge. In the early post-operative period, pain is primarily controlled with a combination of modalities including cryotherapy, narcotic and non-steroidal analgesia. To our knowledge, the use of TENS as an adjunct to post-operative analgesia in the setting of outpatient knee arthroscopy has not been studied extensively. To this end, we propose the following hypothesis:

Hypothesis: Following standard of care procedures for arthroscopy knee surgery it is anticipated that Transcutaneous Electrical Nerve Stimulation (TENS) will provide improved pain relieve and improve functional outcomes.

Specific Aim 1: Determine patient's perception of pain in the early post-operative period while utilizing structure TENS therapy.

Specific Aim 2: Determine the short-term (6 months) outcomes following knee arthroscopy while using TENS in the early post-operative period.

Specific Aim 3: Determine effect of early TENS use on quadriceps strength and tone in the early and intermediate post-operative periods.

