Appendix B. Physician-entered Data at each evaluation

Participant ID # _____

Time	ROM (R/L)	Effusion (R/L)	Strength (R/L)	Quad Circ (R/L)	Other
Pre-op					
1 week					
2 weeks					
6 weeks					
12 weeks					

6 months					
-----------------	--	--	--	--	--

- ROM ("3-0-135")
- Effusion (none, 1+, 2+, 3+)
- Strength (lbs) using hand-held dynamometer
- Thigh circumference (cm) measured 10 cm proximal to superior pole of the patella Other comments

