Appendix E. Timing of Data Collection

Time	Surveys	Clinical Data
Preoperative	SF-12 Marx KOOS Lysholm IKDC Pain VAS	ROM Effusion Strength Quad circ
Intraoperative	IKDC Surgical Document Form	Surgical Data
1 day-14 days	Pain VAS Medication Use	
1 week	See above	ROM Effusion Strength Quad circ
2 weeks	See above	ROM Effusion Strength Quad circ
6 weeks	SF-12 Marx KOOS Lysholm IKDC Pain VAS Medication Use	ROM Effusion Strength Quad circ

12 weeks	SF-12 Marx KOOS Lysholm IKDC Pain VAS Medication Use	ROM Effusion Strength Quad circ
6 months	SF-12 Marx KOOS Lysholm IKDC Pain VAS Medication Use	ROM Effusion Strength Quad circ

**Appendix F. 2000 IKDC Surgical Documentation Form Appendix G. Outcomes Instruments
(SF-12, KOOS, IKDC, Lysholm, Marx)**

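### Does the pain-log analysis planned for months 3-9 put the blinding of the later visits at risk?

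*Combined protocol and SAP*

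**What the plan says.** Section 9.0 (Proposed Timeline) gives three relevant steps: "0-3 months: Patient enrollment begins", then "3-9 months: Data collection. Initial data analysis of immediate post-operative pain logs", then "9-12 months: Data analysis". The power analysis for the multi-center trial comes in months 12-14. No date is given for the close of enrolment.

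On blinding, the Abstract states: "Patients and the surgeon will be blinded to the TENS treatment group". It attaches no end date. Section 7.0 adds a sham arm of 10 against an active arm of 10, sealed envelopes for the assignments, and this on who produces them: "Patients will be randomized using a block randomization scheme generated by the statistician".

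The diary and the TENS treatment both stop at two weeks (Abstract; Appendix D). The later outcomes belong to Aims 2 and 3, for example "Specific Aim 2: Determine the short-term (6 months) outcomes following knee arthroscopy". Appendix E repeats the same set of surveys at 6 weeks, 12 weeks and 6 months: "SF-12 Marx KOOS Lysholm IKDC Pain VAS Medication Use". Appendix B has a physician enter range of motion, effusion grade, thigh circumference and "Strength (lbs) using hand-held dynamometer" at the same visits.

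The documents do not say whether the first pain-log analysis is pooled or by arm, who runs it, or who receives it.

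**The concern.** The pain logs are the Aim 1 data, and their first analysis shares a line of the timeline with continuing data collection. Several outcomes still to come are open to expectation: strength depends on effort and on the examiner's resistance, effusion is graded by eye and hand, and the questionnaires are the patient's own report. If the surgeon, an assessor or a patient learned how the arms compared on pain, and also knew or could work out who was in which arm, the Aim 2 and Aim 3 comparisons could shift. With 10 patients per arm, a listing of diaries by arm would be easy to match to individuals. The plan describes no stopping rule or adaptation that needs an early by-arm result, so the exposure appears to buy little. A reader who expects a written access rule for any analysis before the last visit will notice that there is none.

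**Working it through.** The plan states no figure to reproduce. Two checks matter: how much follow-up is outstanding when the early analysis could happen, and what would have to occur for that analysis to bias the comparison.

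**1. Overlap with later visits**

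Inputs: 20 patients (Section 7.0); later visits at 6, 12 and 26 weeks (Appendix E), which are 1.38, 2.76 and 5.98 months; a diary of 14 days, or 0.46 months (Appendix D). Assumption: even accrual over *A* months, with *A* = 3 as the reading of Section 9.0 and *A* = 6 as a slower case.

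Visits of type *v* outstanding at month *T* = 20 × (*A* + *v* − *T*)/*A*, held between 0 and 20, then summed over the three visits (60 in all).

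For *A* = 3 and *T* = 3.5:
- 6 weeks: 20 × (3 + 1.38 − 3.5)/3 = 5.9
- 12 weeks: 20 × (3 + 2.76 − 3.5)/3 = 15.1
- 6 months: held at 20
- Total: about 41 of 60 (68%)

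| Month of look | Outstanding, *A* = 3 | Outstanding, *A* = 6 |
|---|---|---|
| 3.5 | 40.9 | not computed |
| 4 | 34.3 | not computed |
| 5 | 25.1 | not computed |
| 6 | 19.9 | 33.7 |
| 7 | 13.2 | not computed |
| 8 | 6.5 | 15.8 |
| 9 | 0.0 | 9.9 |

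Counting whole patients gives 35 rather than 34.3 at month 4; the difference is rounding. With *A* = 3 the last diary closes at 3 + 0.46 = 3.46 months and the last 6-month visit falls at 3 + 5.98 = 8.98 months. So within the stated window the exposed share runs from 68% to none, depending on a date the plan does not fix.

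**2. Is Aim 1 affected?**

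Not by a look made after the diaries close, since treatment and diary end together. Diaries still open at month *T* number 20 × (*A* + 0.46 − *T*)/*A*: at month 3 with *A* = 3, 20 × 0.46/3 = 3.1; at month 6 with *A* = 6, 20 × 0.46/6 = 1.5. A look that early would be incomplete, but no decision in the plan depends on it.

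**3. What bias would require**

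Suppose that knowing the pain result makes an assessor or patient score someone believed to be on active TENS higher by δ. Let *g* be the probability that the belief is right, the same in both arms. The mean shift is *g*δ in the active arm and (1 − *g*)δ in the sham arm, so

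bias in the difference = *g*δ − (1 − *g*)δ = (2*g* − 1)δ.

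- If allocation is unknown, *g* = 0.5 and the bias is zero, however striking the pain result.
- If allocation is fully known, *g* = 1 and the bias is δ.

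A general shift in expectation that ignores allocation falls on both arms and cancels. Harm therefore needs a chain: the look is by arm, it is passed to blinded people, and individual allocations are revealed to them or guessed better than chance. Section 9.0 states none of these. Passing allocations to the surgeon or to patients would contradict the Abstract.

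**The case for a change.** The strongest case for a change is that the gap is real and cheap to close. Sham and envelopes protect assignment and treatment; neither governs who sees results afterwards. The Abstract names only patients and the surgeon, so a separate physician or other assessor taking the Appendix B measurements is not expressly covered. At 10 per arm, a casually shared table could reveal individuals. The pilot will inform a larger trial, so a distorted Aim 2 or Aim 3 result could carry forward. One sentence would suffice: the statistician runs any early by-arm analysis and releases nothing by arm until the last visit is entered.

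Most of this is fair as description. The plan is silent on access, assessors other than the surgeon are not named, and patients who have guessed their arm correctly could be influenced by a leaked result. What does not stand is the step from silence to an unprotected blind. The proposed sentence mainly writes down what a blind lasting through follow-up already requires, and the statistician can run the comparison without passing it on.

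The larger remedy, limiting months 3-9 to a pooled check and moving the by-arm comparison to months 9-12, would delay a planned result by up to about 9 − 3 = 6 months. If accrual took six months, the last visit would fall at 6 + 5.98 = 11.98 months, the very end of the analysis window. That cost is certain; the benefit depends on events the plan does not describe.

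**Conclusion.** No change is needed. The timing overlap is confirmed: under even three-month accrual, about 41 of 60 later visits are outstanding at month 3.5, about 20 at month 6 and none at month 9, with more outstanding if accrual is slower. These are counts of visits that could be exposed, not estimates of bias, and they rest on an accrual pattern and an analysis date that the documents do not give. A study run as written, with patients and the surgeon kept blinded through follow-up, gives sound Aim 2 and Aim 3 comparisons as far as this point goes, because the early pain result biases the difference between arms only when allocations are known or guessed better than chance. The missing access rule is a detail that the statistician fills sensibly by keeping by-arm results, listings and codes from the surgeon, assessors and patients until the last 6-month visit. The conclusion would differ if the plan called for sharing by-arm listings during follow-up; it does not.

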Appendix A. Enrollment Screening

NAME _____ Participant ID # _____

Question	Yes	No
Is patient age less than 18 or greater than 60?		
Did patient refuse to sign informed consent?		
Is patient BMI > 50?		
Is the patient receiving simultaneous bilateral surgical treatment?		
Is any knee joint malalignment present?		
Is there any significant joint space narrowing present?		
Has the patient had prior significant knee surgery?		
Does this surgery involve a worker's compensation claim?		

		
Are there reasons the patient will not be able to keep postoperative appointments?		

If any question is answered with “YES”, the patient should not be included in this study.

Appendix B. Physician-entered Data at each evaluation

Participant ID # _____

Time	ROM (R/L)	Effusion (R/L)	Strength (R/L)	Quad Circ (R/L)	Other
Pre-op					
1 week					
2 weeks					
6 weeks					
12 weeks					

6 months					
-----------------	--	--	--	--	--

- ROM ("3-0-135")
- Effusion (none, 1+, 2+, 3+)
- Strength (lbs) using hand-held dynamometer
- Thigh circumference (cm) measured 10 cm proximal to superior pole of the patella Other comments

Appendix C. Preoperative Patient Form

Participant ID # _____

Thank you for agreeing to participate in this important study about the pain control after knee arthroscopy surgery. Please answer the following questions.

1. Are you currently taking pain medication for your knee?

Yes

No

2. If yes, what medication are you taking for your knee pain?

Over the counter (Tylenol, Aleve, Motrin, etc...)

Prescribed anti-inflammatory medication (Celebrex, Ibuprofen, etc...)

Narcotic medication (Vicodin, Percocet, Codeine, etc...)

Steroid medication (Cortisone, Prednisone, etc....)

Other _____

3. During the past week, how often have you taken these medications?

Three or more times a day

Once or twice a day

Once every couple of days

Once a week

Have not taken in the past week 4.

How much pain are you having today?

Please mark on the line where your current pain level is.

No 0 1 2 3 4 5 6 7 8 9 10 Severe
Pain

Pain

Thank you. Please complete the surveys on the following pages.

Appendix D. Patient Pain Diary

Participant ID #: _____

Find your pain level number from the scale below. Enter the number that best represents your pain level for each time listed.

No 0 1 2 3 4 5 6 7 8 9 10 Severe
Pain

Pain

Time	Pain Number (0-10)	Number of Pain Pills since last entry	To Do	Complete (X)
Surgery				
5:00 PM				

8:00 PM				
Day 1				
9:00 AM			TREATMENT	
9:30 AM				
12:00 PM				
3:00 PM			TREATMENT	
3:30 PM				
6:00 PM				
9:00 PM			TREATMENT	
9:30 PM				
Day 2				
9:00 AM			TREATMENT	
9:30 AM				
12:00 PM				
3:00 PM			TREATMENT	
3:30 PM				
6:00 PM				
9:00 PM			TREATMENT	
9:30 PM				
Day 3				
9:00 AM			TREATMENT	
9:30 AM				
12:00 PM				

3:00 PM			TREATMENT	
3:30 PM				

6:00 PM				
9:00 PM			TREATMENT	
9:30 PM				
Day 4				
9:00 AM			TREATMENT	
9:30 AM				
12:00 PM				
3:00 PM			TREATMENT	
3:30 PM				
6:00 PM				
9:00 PM			TREATMENT	
9:30 PM				
Day 5				
9:00 AM			TREATMENT	
9:30 AM				
12:00 PM				
3:00 PM			TREATMENT	
3:30 PM				
6:00 PM				
9:00 PM			TREATMENT	
9:30 PM				
Day 6				
9:00 AM			TREATMENT	
9:30 AM				
12:00 PM				

3:00 PM			TREATMENT	
3:30 PM				
6:00 PM				
9:00 PM			TREATMENT	
9:30 PM				
Day 7				
9:00 AM			TREATMENT	
9:30 AM				
12:00 PM				
3:00 PM			TREATMENT	
3:30 PM				
6:00 PM				
9:00 PM			TREATMENT	
9:30 PM				
Day 8				
9:00 AM			TREATMENT	
9:30 AM				
12:00 PM				
3:00 PM			TREATMENT	
3:30 PM				
6:00 PM				
9:00 PM			TREATMENT	
9:30 PM				
Day 9				
9:00 AM			TREATMENT	

9:30 AM				
12:00 PM				
3:00 PM			TREATMENT	
3:30 PM				
6:00 PM				
9:00 PM			TREATMENT	
9:30 PM				

Day 10				
9:00 AM			TREATMENT	
9:30 AM				

12:00 PM				
3:00 PM			TREATMENT	
3:30 PM				
6:00 PM				
9:00 PM			TREATMENT	
9:30 PM				
Day 11				
9:00 AM			TREATMENT	
9:30 AM				
12:00 PM				
3:00 PM			TREATMENT	
3:30 PM				
6:00 PM				
9:00 PM			TREATMENT	
9:30 PM				

Day 12				
9:00 AM			TREATMENT	
9:30 AM				
12:00 PM				
3:00 PM			TREATMENT	
3:30 PM				
6:00 PM				
9:00 PM			TREATMENT	
9:30 PM				
Day 13				
9:00 AM			TREATMENT	
9:30 AM				
12:00 PM				
3:00 PM			TREATMENT	
3:30 PM				
6:00 PM				
9:00 PM			TREATMENT	
9:30 PM				
Day 14				
9:00 AM			TREATMENT	
9:30 AM				
12:00 PM				
3:00 PM			TREATMENT	
3:30 PM				
6:00 PM				
9:00 PM			TREATMENT	

9:30 PM				
---------	--	--	--	--

Appendix E. Timing of Data Collection

Time	Surveys	Clinical Data
Preoperative	SF-12 Marx KOOS Lysholm IKDC Pain VAS	ROM Effusion Strength Quad circ
Intraoperative	IKDC Surgical Document Form	Surgical Data
1 day-14 days	Pain VAS Medication Use	
1 week	See above	ROM Effusion Strength Quad circ
2 weeks	See above	ROM Effusion Strength Quad circ
6 weeks	SF-12 Marx KOOS Lysholm IKDC Pain VAS Medication Use	ROM Effusion Strength Quad circ

12 weeks	SF-12 Marx KOOS Lysholm IKDC Pain VAS Medication Use	ROM Effusion Strength Quad circ
6 months	SF-12 Marx KOOS Lysholm IKDC Pain VAS Medication Use	ROM Effusion Strength Quad circ

**Appendix F. 2000 IKDC Surgical Documentation Form Appendix G. Outcomes Instruments
(SF-12, KOOS, IKDC, Lysholm, Marx)**
